## **8.2. Medications to be Used with Caution**

### **8.2.1. CYP3A Inhibitors/Inducers**

Ibrutinib is metabolized primarily by CYP3A. Avoid co-administration with strong CYP3A4 inhibitors (eg, ketoconazole, indinavir, nelfinavir, ritonavir, saquinavir, clarithromycin, telithromycin, itraconazole, nefazadone, and cobicistat) and consider alternative agents with less CYP3A inhibition. If the benefit outweighs the risk and a strong CYP3A inhibitor must be used: a) for voriconazole and posaconazole (at doses less than or equal to suspension 200 mg twice daily [BID]), reduce ibrutinib to 140 mg once daily; b) for posaconazole at higher doses (suspension 200 mg three times daily or 400 mg BID, IV injection 300 mg once daily, delayed-release tablets 300 mg once daily) or other strong CYP3A4 inhibitors used short-term (such as anti-infectives for seven days or less), interrupt ibrutinib. If a moderate CYP3A inhibitor (eg, fluconazole, erythromycin, amprenavir, aprepitant, atazanavir, ciprofloxacin, crizotinib, diltiazem, fosamprenavir, imatinib, verapamil, amiodarone, and dronedarone) must be used, reduce ibrutinib to 280 mg for the duration of the inhibitor use. No dose adjustment is required in combination with mild inhibitors. Subjects should be monitored for signs of ibrutinib toxicity. Avoid grapefruit and Seville oranges during ibrutinib treatment, as these contain strong or moderate inhibitors of CYP3A (see Section 6). Recommended dose modifications for ibrutinib when co-administered with CYP3A inhibitors are summarized in [Attachment 5](#).

Avoid concomitant use of strong CYP3A inducers (eg, carbamazepine, rifampin, phenytoin, and St. John's Wort).

A list of CYP3A inhibitors and inducers can be found in [Attachment 3](#) and at <http://medicine.iupui.edu/clinpharm/ddis/table.aspx>. This website is continually revised and should be checked frequently for updates. For the most comprehensive effect of CYP3A inhibitors or inducers on ibrutinib exposure, please refer to the current version of the IB.

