#### **6. DOSAGE AND ADMINISTRATION**

Ibrutinib will be administered orally, once daily, at a dose of 420 mg (140 mg × 3 capsules taken together at one time). Protocol-specified dose modifications of ibrutinib will be made as

necessary. Study drug (3 capsules) is administered orally once daily with approximately 8 ounces (240 mL) of water. The capsules should be swallowed whole and should not be opened, broken, or chewed. The use of strong CYP3A inhibitors/inducers, and grapefruit and Seville oranges should be avoided for the duration of the study (Section 8.2 and Attachment 3).

If a dose is not taken at the scheduled time, it can be taken as soon as possible on the same day with a return to the normal schedule the following day. The subject should not take extra capsules to make up the missed dose. Missed doses of study drug will not be made up.

The first dose will be administered in the clinic on Day 1 of Week 1, after which study drug will be self-administered daily by the subjects on an outpatient basis. Study drug will be dispensed to subjects in bottles. Unused study drug dispensed during previous visits must be returned to the site and drug accountability records (Section 14.5) updated at each visit. Returned capsules must not be re-dispensed to anyone.

Study drug dosing is continuous (without interruptions) throughout the Treatment Phase.

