**Table 2: Study Drug Dose Modifications**

Occurrence	Action
First	Withhold study drug until recovery to Grade $\leq 1$ or baseline; may restart at original dose level
Second	Withhold study drug until recovery to Grade $\leq 1$ or baseline; may restart at 1 dose level lower (ie, 280 mg/day/2 capsules)
Third	Withhold study drug until recovery to Grade $\leq 1$ or baseline; may restart at 1 dose level lower (ie, 140 mg/day/1 capsule)
Fourth	Discontinue ibrutinib a

a. If the oral study drug is discontinued for toxicity, subject will end the Treatment Phase of the study.

Please see Section [8.2.1](#) for guidelines for management of study drug in subjects who require treatment with a strong CYP3A inhibitor.

Once there has been a dose reduction of ibrutinib, there will be no dose re-escalations. No dose escalation of ibrutinib (above 420 mg) is allowed in this study.

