**Attachment 5: Recommended Dose Modifications of Ibrutinib for Use with CYP3A Inhibitors**

Patient Population	Co-administered Drug	Recommended Ibrutinib Dose for the Duration of the Inhibitor Use a
B-Cell Malignancies	Mild CYP3A inhibitors	420 mg or 560 mg once daily per indication. No dose adjustment required.
	Moderate CYP3A inhibitors	280 mg once daily.
	
 
• Voriconazole
 
• Posaconazole at doses less than or equal to suspension 200 mg BID
 
	140 mg once daily.
	
 
• Other strong CYP3A inhibitors
 
• Posaconazole at higher dosesb
 
	Avoid concomitant use and consider alternative with less CYP3A inhibitory potential If these inhibitors will be used short-term (such as anti-infectives for seven days or less), interrupt ibrutinib.

a. Monitor for adverse reactions to ibrutinib and interrupt or modify dose as recommended.

b. Posaconazole at higher doses (posaconazole suspension 200 mg three times daily or 400 mg twice daily, posaconazole IV injection 300 mg once daily, posaconazole delayed-release tablets 300 mg once daily).

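### With a moderate CYP3A inhibitor the protocol states a flat 280 mg; for a subject already reduced to 280 or 140 mg that equals or doubles the current dose, and the doubling conflicts with the no-re-escalation rule.

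*Protocol*

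**What the plan says.** Protocol Section 6 sets the study dose: "Ibrutinib will be administered orally, once daily, at a dose of 420 mg (140 mg × 3 capsules taken together at one time").

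Table 2 in Section 6.4 gives the steps for drug-related toxicity. After the first occurrence the original dose may be resumed. After the second the subject "may restart at 1 dose level lower (ie, 280 mg/day/2 capsules"). After the third the subject "may restart at 1 dose level lower (ie, 140 mg/day/1 capsule"). Below the table stands: "Once there has been a dose reduction of ibrutinib, there will be no dose re-escalations". The table's pointer to Section 8.2.1 mentions strong CYP3A inhibitors only.

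Section 8.2.1 covers CYP3A inhibitors. For a moderate inhibitor that must be used, the site is to "reduce ibrutinib to 280 mg for the duration of the inhibitor use". For voriconazole, or posaconazole up to a stated dose, it is to "reduce ibrutinib to 140 mg once daily". Higher-dose posaconazole and other strong inhibitors are to be avoided, or ibrutinib interrupted if their use is short. Mild inhibitors need no adjustment.

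Attachment 5 summarises these rules in a column headed "Recommended Ibrutinib Dose for the Duration of the Inhibitor Use". The moderate-inhibitor row reads "280 mg once daily". There is no column or footnote for the subject's current dose or for an earlier reduction.

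Section 6.5 separately recommends 140 mg daily for Child-Pugh class A. Exclusion criterion 17 bars only classes B and C, so class A subjects can enter.

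**The concern.** The inhibitor doses are absolute amounts. They act as reductions from 420 mg, but the protocol's own rules place some subjects below 420 mg before an inhibitor is started. For a moderate inhibitor the stated amount then stops being a reduction, and no passage says how the two adjustments combine.

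The subjects concerned have already had repeated drug-related toxicity, or have hepatic impairment, and are starting a drug for which Section 8.2.1 calls for less ibrutinib. A site that goes to the summary table for the answer finds, for a subject on 140 mg, a dose that another section forbids.

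The overlap is plausible. Exclusion criterion 21 bars subjects who need a strong inhibitor but not those who need a moderate one. The moderate inhibitors named in Section 8.2.1 include anti-infectives, an anti-emetic and anti-arrhythmics, while Section 6.4 deals with neutropenia with infection, persistent nausea or vomiting, and atrial fibrillation.

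**Working it through.** **Inputs.** Capsule strength 140 mg and study dose 420 mg (Section 6); steps to 280 mg and 140 mg (Table 2, Section 6.4); 140 mg for Child-Pugh A (Section 6.5); 280 mg with a moderate inhibitor, and 140 mg with voriconazole or lower-dose posaconazole (Section 8.2.1, Attachment 5).

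**The plan's own dose levels.** 3 × 140 = 420 mg, 2 × 140 = 280 mg, 1 × 140 = 140 mg. These agree with Section 6 and Table 2.

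**Formula.** Ratio = stated inhibitor dose ÷ subject's current dose.

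| Current dose | Moderate inhibitor (280 mg) | Voriconazole or lower-dose posaconazole (140 mg) |
|---|---|---|
| 420 mg | 280/420 = 0.67 | 140/420 = 0.33 |
| 280 mg (second toxicity) | 280/280 = 1.00 | 140/280 = 0.50 |
| 140 mg (third toxicity, or Child-Pugh A) | 280/140 = 2.00 | 140/140 = 1.00 |

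At full dose both rules reduce the dose, by one third and by two thirds. In the four cells below full dose, one is doubled, two are unchanged and one is halved. Both moderate-inhibitor cells are unchanged or doubled. The remaining classes carry an instruction to avoid or interrupt, or no adjustment, and so raise no such ratio.

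**The passages side by side, for a subject at 140 mg after a third toxicity who must take a moderate inhibitor.**

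- Attachment 5 gives 280 mg.
- Section 8.2.1 says to reduce to 280 mg, which is impossible from 140 mg.
- Section 6.4 allows no re-escalation after a reduction, so 280 mg is barred.

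The three cannot all be followed.

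**For a subject at 140 mg under Section 6.5.** Section 6.5 and Attachment 5 again give different doses. It is also unclear whether a hepatic dose counts as a reduction that brings the no-re-escalation rule into play.

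**After the inhibitor stops.** Sections 8.2.1 and Attachment 5 tie the lower dose to the period of inhibitor use, which implies a return afterwards. The rule under Table 2 makes no exception for reductions made because of an inhibitor.

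**Effect on a reported quantity.** SAP Section 2.9 takes 420 mg as the assigned dose in relative dose intensity unless it is modified for a CYP3A inhibitor. A subject held at 280 mg for toxicity scores 280/420 = 67%. If a moderate inhibitor is added and the assigned dose becomes 280 mg, the same intake scores 280/280 = 100% for that period, although the toxicity reduction is still in force.

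**The case against.** The strongest reply is that the protocol, read as a whole, does not tell anyone to double a dose. Section 8.2.1 uses the verb reduce, Attachment 5 is described there as a summary, and the sentence under Table 2 bars re-escalation. This stands: a reader might infer that the protocol orders a doubling, and the documents do not support that. What they show is a conflict between provisions. The reply does not remove it, because Attachment 5 repeats neither limit, Table 2 points to Section 8.2.1 only for strong inhibitors, and a bar on increases says nothing about the subject at 280 mg.

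A reader might also infer that every inhibitor class is affected. That is not so: voriconazole or lower-dose posaconazole halves a 280 mg dose, and other strong inhibitors lead to avoidance or interruption. The mild row of Attachment 5 prints full doses, but it says no adjustment is needed, so it should not be read as restoring them.

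Third, an unchanged dose is an error only if each inhibitor adjustment must be a cut from the current dose, and no passage says so. An absolute dose may be acceptable on clinical-pharmacology grounds; Section 8.2.1 refers to the Investigator's Brochure, which is not available here. This stands too. The unchanged cells show that the plan is silent, not that the dose is wrong. The documents also speak of drug-related toxicity, so it should not be inferred that these subjects have shown intolerance that depends on dose.

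Fourth, toxicity monitoring is required, and footnote a of Attachment 5 allows interruption or modification. Both are general and do not say which provision governs.

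Last, few of about 17 subjects are likely to be affected. That is fair; the documents give no frequency for the combination.

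**Conclusion.** The point holds for moderate inhibitors. The stated 280 mg is 100% of the current dose for a subject at 280 mg and 200% for a subject at 140 mg, compared with 67% at full dose. The 200% case contradicts Section 6.4 when the 140 mg dose came from toxicity, and disagrees with Section 6.5 when it came from Child-Pugh A impairment. The 100% case is a gap: nothing says whether the toxicity step already taken suffices.

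This rests on taking the doses as printed and on no rule for combining them existing elsewhere in the two documents; none was found. The Investigator's Brochure may contain one, but the protocol does not point to it for this purpose.

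The issue concerns subject safety and clarity for sites and should be corrected. It does not bear on the primary response rate or its test. The only analysis effect identified is on relative dose intensity, a descriptive exposure summary.

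**What to change.** Reconcile Table 2 and the sentence below it (Section 6.4), Section 6.5, Section 8.2.1 and Attachment 5.

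- Add a footnote to Attachment 5 saying which provision governs when a subject already below 420 mg, for toxicity or hepatic impairment, starts a listed inhibitor.
- State how the no-re-escalation rule applies: whether it limits the Attachment 5 dose, whether it covers a hepatic dose, and whether it covers the return after an inhibitor is stopped.
- Add matching cross-references in Sections 6.4, 6.5 and 8.2.1, and widen the one below Table 2 to include moderate inhibitors.
- Once this is settled, say in SAP Section 2.9 which assigned dose applies when both adjustments are in force.

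The clinical rule is for the sponsor to set; no dose is proposed here. The cost is one footnote, a few cross-references and one SAP sentence, carried in a protocol amendment. No new data, visits or subjects are needed.

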### **8.2.2. Drugs That May Have Their Plasma Concentrations Altered by Ibrutinib**

In vitro studies indicated that ibrutinib is a weak reversible inhibitor toward CYP2B6, CYP2C8 CYP2C9, CYP2C19, CYP2D6, and CYP3A4/5 and does not display time-dependent CYP inhibition. The dihydrodiol metabolite of ibrutinib is a weak inhibitor toward CYP2B6, CYP2C8, CYP2C9, and CYP2D6. Both ibrutinib and the dihydrodiol metabolite are at most weak inducers of CYP450 isoenzymes in vitro. Therefore, it is unlikely that ibrutinib has any clinically relevant drug-drug interactions with drugs that may be metabolized by the CYP450 enzymes.

Ibrutinib is a mild inhibitor of P-gp and breast cancer resistance protein (BCRP). Ibrutinib is not expected to have systemic drug-drug interactions with P-gp substrates. However, it cannot be excluded that ibrutinib could inhibit intestinal P-gp after a therapeutic dose. There are no clinical data available. To minimize the potential interaction in the GI tract, narrow therapeutic range P-gp substrates such as digoxin, should be taken at least 6 hours before or after ibrutinib. Ibrutinib may also inhibit BCRP systemically and increase the exposure of drugs that undergo BCRP-mediated hepatic efflux, such as rosuvastatin.

### **8.2.3. Concomitant Use of Antiplatelet Agents and Anticoagulants**

Warfarin or other vitamin K antagonists as well as supplements such as fish oil and vitamin E preparations should be avoided. Use ibrutinib with caution in subjects requiring anticoagulants or medications that inhibit platelet function. Subjects with congenital bleeding diathesis have not been studied. Ibrutinib should be held at least 3 to 7 days pre- and post-surgery depending upon the type of surgery and the risk of bleeding (see Section 8.4).

Subjects requiring the initiation of therapeutic anticoagulation therapy (eg, atrial fibrillation), consider the risks and benefits of continuing ibrutinib treatment. If therapeutic anticoagulation is clinically indicated, treatment with ibrutinib should be held and not be restarted until the subject is clinically stable and has no signs of bleeding. No dose reduction is required when study drug is restarted. Subjects should be observed closely for signs and symptoms of bleeding.

### **8.3. Prohibited Concomitant Medications**

Any other chemotherapy, anticancer immunotherapy, experimental therapy, or radiotherapy are prohibited while the subject is receiving study drug.

Corticosteroids for the treatment of the underlying disease are prohibited. Please refer to Section 8.1 for corticosteroid use in other medical situations.

The Sponsor must be notified in advance (or as soon as possible thereafter) of any instances in which use of prohibited therapies are considered.

### **8.4. Procedures**

The following guidance should be applied during the perioperative period for subjects who require surgical intervention or an invasive procedure while receiving study drug.

#### **8.4.1. Minor Surgical Procedures**

For minor procedures (such as a central line placement, needle biopsy, lumbar puncture [other than shunt reservoir access] thoracentesis, or paracentesis) study drug should be held for at least 3 days prior to the procedure and should not be restarted for at least 3 days after the procedure. For bone marrow biopsies that are performed while the subject is on study drug, it is not necessary to hold study drug.

#### **8.4.2. Major Surgical Procedures**

For any surgery or invasive procedure requiring sutures or staples for closure, study drug should be held at least 7 days prior to the intervention and should be held at least 7 days after the procedure and restarted at the discretion of the investigator when the surgical site is reasonably healed without serosanguineous drainage or the need for drainage tubes.

#### **8.4.3. Emergency Procedures**

For emergency procedures, study drug should be held after the procedure for at least 7 days after the urgent surgical procedure.

### **8.5. Plasmapheresis**

Management of hyperviscosity in WM patients may include plasmapheresis before and during treatment with study drug. Modifications to the dosing of study drug are not required.

In the event that a subject requires plasmapheresis prior to study treatment, the IgM level obtained prior to plasmapheresis should be considered as the baseline value and study drug should be initiated shortly thereafter (not more than 7 days) after last plasmapheresis. IgM level obtained within five half-lives (ie,  $\leq 35$  days) after the last plasmapheresis should not be considered for response evaluation. An IgM level obtained more than 35 days after plasmapheresis can be used in response determination. The IgM level prior to and after each plasmapheresis during the screening phase and during the study should be collected centrally and will be recorded in the eCRF.

## **9. STUDY EVALUATIONS**

### **9.1. Study Procedures**

#### **9.1.1. Overview**

The study is divided into a Screening Phase, a Treatment Phase, and a Follow-up Phase. The **TIME AND EVENTS SCHEDULE** summarizes the frequency and timing of efficacy, PK, and safety measurements applicable to this study. All subjects enrolled will undergo the same study procedures throughout the study unless otherwise noted.

The total blood volume to be collected estimated is approximately 30 mL for the Screening Phase, 72 mL from Week 1 to Week 24, 12 mL every 8 weeks from Week 25, 15 mL at the suspected PD visit, 15 mL at the End-of-Treatment (EOT) Visit, and 7 mL every 12 weeks for the Post-treatment Pre-disease Progression Phase. Repeat or unscheduled samples may be taken

for safety reasons or for technical issues with the samples. The volume of blood to be drawn is considered to be normal and acceptable for subjects participating in a cancer clinical study and is deemed reasonable over the time frame of the study.

### **9.1.2. Screening Phase**

Screening procedures will be performed up to 30 days prior to Day 1 of Week 1, unless otherwise specified. All subjects must first read, understand, sign and date the ICF before any study-specific screening procedures are performed. Clinicopathological diagnosis of WM must be confirmed by a central laboratory for all subjects before enrollment.

Unless specified otherwise, all study tests and procedures should be performed at the study center at which the subject was enrolled and will be receiving treatment. After signing the ICF, screening, and being deemed eligible for entry, subjects will be enrolled in the study. Refer to the **TIME AND EVENTS SCHEDULE** for a complete list of procedures to be performed at Screening.

### **9.1.3. Treatment Phase**

Details of the procedures performed during the treatment phase are outlined in the **TIME AND EVENTS SCHEDULE**. The latest measurements taken on Day 1 of Week 1 before administration of study drugs or at screening will be defined as the baseline values. Clinical evaluations and laboratory studies may be repeated more frequently, if clinically indicated. If a subject shows signs of progression on physical examination or laboratory assessment, a suspected PD visit should be scheduled and the subject may continue study treatment until progression is confirmed. If progressive disease is diagnosed, the subject will discontinue study drug, complete the EOT Visit and enter the Follow-up Phase.

#### ***Suspected PD Visit***

The Suspected PD visit should be performed at any time during the study, if based on clinical and/or laboratory evaluation, the investigator suspects progressive disease (PD), or if the subject discontinues treatment for any other reason. If possible, the visit should be performed within 24 hours after the subject's previous dose.

#### ***End of Treatment Visits***

Unless a subject withdraws consent for study participation, died, or is lost to follow-up, the EOT visit should occur 30 days ( $\pm$  7 days) from the last dose of study drug or prior to the start of a new anticancer treatment. If the subject starts a new anticancer treatment less than 7 days after the Suspected PD visit, only those procedures not conducted at the Suspected PD visit should be performed at the EOT visit. Refer to **TIME AND EVENTS SCHEDULE** for procedures to be performed at the EOT visit.

Every effort should be made to conduct the EOT visit before the subject starts subsequent treatment. If a subject is unable to return to the site for the EOT visit, then the subject should be contacted to collect information on adverse events that occur up to 30 days after the last dose of

study treatment. Additional information on reporting of adverse events is presented in Section 12.

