Quantitative serum immunoglobulins (IgA, IgG and IgM)	X	X	X	X	X	X	X	X	X	
Serum free light chain assay	X					Weeks 49 and 97	X			
Bone marrow aspirate and biopsy l	X					Weeks 49 and 97 (± 2 weeks)	X	X		

	Screening Phase	Treatment Phase							Post-Treatment/ Follow-Up Phase	
		1	5-16 q4 weeks	17	21	25+ q8 weeks	Suspected PD Visit	End-of-Treatment Visit a	Post-treatment Pre-disease Progression Phase q12 weeks	Post-disease Progression Phase q12 weeks
Study Weeks		1	5-16 q4 weeks	17	21	25+ q8 weeks	Suspected PD Visit	End-of-Treatment Visit a	Post-treatment Pre-disease Progression Phase q12 weeks	Post-disease Progression Phase q12 weeks
Study Day of the Study Week		1	1	1	1	1				
Study Windows	-30 days		± 3 days		± 3 days	± 3 days	Anytime	± 7 days	± 7 days	± 7 days
CT Scans	X i			X j		X i	X k		X j	
Overall disease assessment			X	X	X	X	X	X	X	
Survival status, new anticancer therapy and occurrence of other malignancy m									X	X
PK sampling										
PK h		X	Weeks 5 and 9							
Ongoing Subject Assessments										
Concomitant medications	X	Continuous from Informed Consent to 30 days after last dose of study drug								
Adverse events	X	Continuous from Informed Consent to 30 days after last dose of study drug								

Abbreviations: aPTT=activated partial thromboplastin time; CR= complete response; CT=computed tomography; DNA=deoxyribonucleic acid; ECG=electrocardiogram; ECOG=Eastern Cooperative Oncology Group; eCRF=electronic case report form; EOT=end-of-treatment; ICF=informed consent form; IEC=Independent Ethics Committee; INR=international normalized ration; IRB=Institutional Review Board; PCR=polymerase chain reaction; PD=progressive disease; PK=pharmacokinetic(s); PO=orally; PT=prothrombin time; q4 weeks=every 4 weeks; q8 weeks=every 8 weeks; q12 weeks=every 12 weeks; REB=research ethics board.

- a. Thirty (30) days from last dose of study drug or prior to the start of a new anticancer treatment.
- b. All subjects must first read, understand, sign and date the IRB/REB/IEC-approved ICF before any study-specific screening procedures are performed.
- c. Physical Examination includes: general appearance of subject, height (screening only) and weight and examination of skin, eyes, ears, nose, throat, lungs, heart, abdomen, extremities, musculoskeletal system, lymphatic system, and nervous system.

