##### **9.1.4.2. Post-disease Progression Phase**

After investigator confirmed disease progression, subjects will be contacted to assess survival status, the use of alternative antineoplastic therapy and occurrence of any other malignancy approximately every 12 weeks ( $\pm 7$  days) by clinic visit or telephone until death, withdrawal by subject, lost to follow-up, or study terminated by Sponsor, whichever comes first. At the time of the primary analysis and at study closure, a survival sweep will be conducted. All subjects who are on study and not known to have died prior to the survival sweep will be contacted at that time.

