### **9.4.1. Adverse Events**

All adverse events will be reported from the time a signed and dated ICF is obtained until 30 days following the last dose of study drug. Adverse events will be reported by the subject (or, when appropriate, by a caregiver, surrogate, or the subject's legally acceptable representative) for the duration of the study. Adverse events will be followed by the investigator as specified in Section 12.

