### 6.1. Adverse Events

The verbatim terms used in the CRF by investigators to identify adverse events will be coded using the Medical Dictionary for Regulatory Activities (MedDRA). Treatment-emergent adverse events (TEAEs) are those adverse events occurring after the first dose of study drugs and within 30 days following the last dose of study drug or initiation of subsequent antineoplastic treatment, whichever occurs earlier; any adverse event that is considered study drug-related regardless of the start date of the event; or any adverse event that is present at baseline but worsens after the first administration of study drug in severity or is subsequently considered drug-related by the investigator. If the event occurs on the day of the initial administration of study agent, and either event time or time of administration are missing, then the event will be assumed to be treatment emergent. If the event date is recorded as partial or completely missing, then the event will be considered to be treatment emergent unless it is known to be prior to the first administration of study agent based on partial onset date or resolution date. All reported treatment-emergent adverse events will be included in the analysis. For each adverse event, the number and percentage of subjects who experience at least 1 occurrence of the given event will be summarized.

Summary tables will be provided for treatment-emergent adverse events:

- Overall summary of all TEAEs
- TEAEs by System Organ Class (SOC), preferred term (PT) and toxicity grade 3 or higher
- TEAE with frequency of at least 10% by SOC, PT and toxicity grade 3 or higher
- Drug-related TEAEs by SOC, PT and toxicity grade 3 or higher
- Serious TEAEs by SOC, PT and toxicity grade 3 or higher
- TEAEs leading to dose modification (including dose interruption and dose reduction) by SOC, PT and toxicity grade 3 or higher
- TEAEs leading to discontinuation of study drug by SOC, PT and toxicity grade 3 or higher
- TEAEs leading to death by SOC and PT
- TEAEs by SOC, PT and toxicity by period
- TEAE of interest for COVID-19 infection by PT and toxicity grade
- Serious TEAE of interest for COVID-19 infection by PT and toxicity grade

- TEAE of interest for COVID-19 infection leading to death by PT

In addition to the summary tables, listings will be provided as appropriate.

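### An End-of-Treatment visit held on days 23 to 29 leaves up to 7 days of the 30-day adverse-event window with no scheduled contact assigned to collect events

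*Protocol*

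**What the plan says.** **Timing of the visit.** Protocol Section 9.1.3 (End of Treatment Visits) states that the visit "should occur 30 days ( $\pm$ 7 days) from the last dose of study drug", or takes place before a new anticancer treatment begins. The EOT column of the Time and Events Schedule carries the same ± 7 days. Its footnote a reads "Thirty (30) days from last dose of study drug or prior to the start of a new anticancer treatment" and sets no earliest day for the second route.

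**Period over which adverse events are collected.** The schedule's adverse-event row is "Continuous from Informed Consent to 30 days after last dose of study drug". Section 9.4.1 likewise runs "until 30 days following the last dose of study drug". Section 12.3.1 gives a different end: the subject's last study-related procedure, which may be a safety follow-up contact.

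**Period over which they are counted.** SAP Section 6.1 (like Protocol Section 11.5) treats an event as treatment-emergent if it occurs "within 30 days following the last dose of study drug or initiation of subsequent antineoplastic treatment", whichever comes first. Drug-related events count whatever their start date.

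**Contacts after the visit.** A subject unable to return for the EOT visit is to be "contacted to collect information on adverse events that occur up to 30 days after the last dose". Under Section 9.1.4.2, after progression, "subjects will be contacted to assess survival status, the use of alternative antineoplastic therapy and occurrence of any other malignancy approximately every 12 weeks". Under Section 9.1.4.1, subjects who stopped for other reasons attend clinic every 12 weeks.

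**The concern.** The visit window is symmetric around the day on which the adverse-event window closes. A site that books day 23 follows the protocol, yet the last week of the window still lies ahead, and nothing in the schedule prompts anyone to ask about it afterwards. The protocol secures a full 30-day enquiry for the subject who does not come back, but not for the one who attends promptly.

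At stake is how evenly the 30-day tail is ascertained. Treatment-emergent, serious treatment-emergent and major-haemorrhage summaries all use that tail. If some subjects are questioned about all 30 days and others about 23, the counts depend partly on how sites book visits. Safety is a secondary objective, and the data are meant to support full approval in China, so the tail should be collected in the same way for everyone who stops treatment.

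**Working it through.** The documents give no figure for this gap, so the check is date arithmetic followed by a comparison of the contacts.

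**Inputs**
- EOT window: 30 ± 7 days after last dose (Protocol Section 9.1.3; Time and Events Schedule).
- End of adverse-event collection: day 30 (schedule; Section 9.4.1).
- End of the treatment-emergent window: day 30 or start of new therapy, whichever is earlier (SAP Section 6.1).
- Planned sample: about 17 subjects (Section 11.2).

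**Step 1. Window.** Earliest in-window visit = 30 − 7 = day 23; latest = 30 + 7 = day 37.

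**Step 2. Days left after the visit.** Days left = max(0, 30 − visit day).

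| EOT visit day | Days of the window left |
|---|---|
| 23 (earliest in-window) | 7 (7/30 = 23.3%) |
| 30 | 0 |
| 37 | 0 |
| 14 (brought forward for new therapy) | 16 |
| 7 (brought forward for new therapy) | 23 |

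The 7-day limit therefore applies only to the ± 7 day window. A visit brought forward for new therapy can leave more. If that therapy starts at once, the time-based treatment-emergent window closes with it. If it is then delayed, the window stays open up to day 30.

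**Step 3. Who is asked about the remaining days?**

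| Subject | Next scheduled contact | Adverse-event enquiry assigned? |
|---|---|---|
| Cannot return for EOT | Contact under Section 9.1.3 | Yes, up to day 30 |
| Attends EOT on day 30 to 37 | The visit itself | Yes, whole window has passed |
| Attends before day 30, progressed | About 12 weeks, clinic or telephone | No; survival, new therapy and other malignancy only |
| Attends before day 30, not progressed | 12-weekly clinic visit | Not assigned; the adverse-event row ends at day 30, though examination, eye symptoms, vital signs and haematology are scheduled |

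**Step 4. Delay before the next contact.** The documents do not say what the 12 weeks are counted from. If from last dose, the first contact falls at 84 ± 7 = day 77 to 91. If from a day-23 EOT visit, it falls at 23 + 84 ± 7 = day 100 to 114. On either assumption, recall of days 24 to 30 would be at least 77 − 30 = 47 days old.

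**Step 5. Weight of one subject.** With 17 subjects, one subject is 1/17 = 5.9 percentage points. SAP Section 6.1 counts subjects with at least one occurrence, so a missed event shifts a percentage by this amount only if it was that subject's sole occurrence of the term. This is the weight of any one subject in any table and is not an estimate of bias.

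**Step 6. After the change.** With no visit before day 30, or a day-30 contact after any earlier visit by a subject not yet on new therapy, the days left fall from at most 7 (in-window) to 0.

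**The case against.** A reader might infer that no later contact can collect adverse events and that these days go unobserved. The documents do not support that:

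- Collection is not tied to the EOT visit. The schedule and Section 9.4.1 keep it open to day 30 whatever the visit date, and Section 12.3.1 carries reporting on to the last study-related procedure.
- The gravest outcomes have their own routes. Serious events are reportable within 24 hours of the site learning of them (Section 12.3.2), as are events of special interest, including major haemorrhage, whatever their seriousness (Section 12.1.4). Deaths within 30 days of last dose must be reported as serious adverse events (Section 12.3.1). Subjects carry a card with a 24-hour number.
- Subjects who stop without progression, including those who stop for toxicity, are seen again in clinic, where events can be recorded retrospectively.
- The target is day 30, and the window allows days 31 to 37 as readily as days 23 to 29. Nothing shows that sites would book early.

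All of this stands, and it limits the point. It does not remove it. Reporting on awareness requires that someone becomes aware, and non-serious events outside special interest are the least likely to be volunteered. The safety contact in Section 12.3.1 is optional, undated and assigned to no visit. It also sits beside a 30-day limit elsewhere with which it disagrees. An open duty to report is weaker than a scheduled question.

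It is also fair to say that the study's safety analysis is descriptive and that the response-rate endpoint is untouched.

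**Conclusion.** The point holds in a limited form. A compliant EOT visit can precede the close of the adverse-event window by up to 7 days. For a subject seen early who has not started new therapy, those days have no scheduled contact assigned to collect events, and capture rests on spontaneous or retrospective reporting. The gap is widest after progression, where the listed contacts do not include adverse events.

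The effect is confined to the descriptive safety tables, and its size is unknown. It depends on how many subjects stop study drug, how many are seen before day 30 without new therapy, and how many events in the remaining days go unreported. The documents give none of these. The 23% is the largest share of the window left after an in-window visit and must not be read as a share of events lost.

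The conclusion rests on two readings: that an enquiry counts as scheduled only if the schedule or the text assigns it to a contact, and that the permissive wording of Section 12.3.1 does not do so. It is worth correcting because the remedy is cheap.

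**What to change.** 1. In Protocol Section 9.1.3 and the EOT column of the Time and Events Schedule, change the window to 30 days (+7 days) after last dose. Keep the provision for an earlier visit before new anticancer treatment.
2. Apply the adverse-event contact that Section 9.1.3 already provides for non-returning subjects, at day 30, to any subject whose EOT visit was before day 30 and who has not started new therapy. This includes visits brought forward for therapy that is then delayed, which the first change alone would not cover.
3. At the same time, reconcile the end of adverse-event reporting: 30 days after last dose in the schedule and Section 9.4.1, against the last study-related procedure in Section 12.3.1.

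The cost is a line of text, a schedule cell and a short addition to the contact rule. No clinic visit is added. Compared with the earliest date now allowed, the visit falls up to a week later, or a short telephone call is made.
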